2.14 Biomarkers

Not applicable.

2.15 Other exploratory analyses

Not applicable

2.16 Interim analysis

Not applicable

3 Sample size calculation

This study is designed to enroll a minimum of 40 patients. Statistical computations were performed (see table below) to evaluate probabilities to observe at least one patient with an AE given 40 patients and different scenarios of AE incidence rates (Hanley and Lippman-Hand 1983). This table shows a reasonable chance to observe AE events occurring with an incidence of 3% or higher together with the 95% Clopper-Pearson confidence interval (CI) for the incidence rate.

Table 3-1 Clopper-Pearson 95% CI for different incidence of AEs and the corresponding probability to observe at least one AE

Incidence of AE	Clopper-Pearson 95% CI for the incidence rate	Probability that at least one patient out of 40 experiences that AE
3%	(0.00, 0.14)	0.70
4%	(0.00, 0.15)	0.80
5%	(0.01, 0.17)	0.87
6%	(0.01, 0.18)	0.92
7%	(0.01, 0.20)	0.95
10%	(0.03, 0.24)	0.99
15%	(0.06, 0.30)	1.00
20%	(0.09, 0.36)	1.00
25%	(0.13, 0.41)	1.00

30%	(0.17, 0.47)	1.00
-----	--------------	------

4 Change to protocol specified analyses

- According to statistical section 10.5.3.2 in the protocol, the number and frequency of overall AEs and gastrointestinal AEs will be summarized for naïve (no ICT prior to enrollment) and non-naïve patients. However, this will not be done. Further, only on-treatment deaths will be summarized instead of all deaths. All deaths will be presented in the listings with post-treatment deaths flagged.
- According to statistical section 10.5.3.4 in the protocol, Data on ECG, vital signs, height, weight, ocular and auditory findings will be listed, summarized and flagged as appropriate. However, ECG, auditory and ocular findings are only listed but not summarized due to the limited amount of data collected (only unscheduled assessments for ECG and mostly EOT visits for ocular and auditory at post baseline).

5 Appendix

This will be used later for drafting CSR Appendix 16.1.9.

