5.3 Exclusion criteria

Patients eligible for this study must not meet **any** of the following criteria:

1. Patients that receive more than one iron chelator at the same time as current iron chelation treatment. (Patients who have received combination therapy in their medical history but are currently being treated with a single ICT agent are eligible.)
2. Patients continuing on deferoxamine or deferiprone in addition to study treatment. (Patients switching to or continuing on deferasirox are eligible).
3. Unresolved adverse events if the patient was previously treated with deferiprone or deferoxamine or deferasirox.

4. Significant proteinuria as indicated by a urinary protein/creatinine ratio $> 0.5 \text{ mg/mg}$ in a non-first void sample urine measured at screening visit 1.
5. Serum creatinine $>$ age adjusted ULN measured at any screening visit
6. Creatinine clearance below 90 mL/minute measured at any screening visit. Creatinine clearance using the Schwartz formula will be estimated from serum creatinine measured at each respective visit.
7. ALT and/or AST $> 2.5 \times \text{ULN}$ measured at screening visit 1.
8. Total bilirubin (TBIL) $> 1.5 \times \text{ULN}$ measured at screening visit 1.
9. Patients with significant impaired GI function or GI disease that may significantly alter the absorption of oral deferasirox FCT (e.g. ulcerative diseases, uncontrolled nausea, vomiting, diarrhea, malabsorption syndrome, or small bowel resection).
10. History of and/or laboratory evidence of active Hepatitis B or Hepatitis C (HBsAg in the absence of HBsAb OR HCV Ab positive with HCV RNA positive).
11. Liver disease with severity of Child-Pugh Class B or C.
12. History of hypersensitivity to any of the study drug or excipients.
13. Patients participating in another clinical trial or receiving an investigational drug.
14. Patients with a known history of HIV seropositivity.
15. Patients unwilling or unable to comply with the protocol.
16. History of malignancy of any organ system, treated or untreated, within the past 5 years whether or not there is evidence of local recurrence or metastases, with the exception of localized basal cell carcinoma of the skin.
17. Significant medical condition interfering with the ability to partake in this study (e.g. uncontrolled hypertension, unstable cardiac disease not controlled by standard medical therapy, systemic disease: cardiovascular, renal, hepatic, etc.).

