7.2.3 Limitations of the study

Novartis will carefully ensure that the PASS will not interfere/modify the local medical practices. The sites will be selected based on their transfusional hemosiderosis treatment experience and patients will be enrolled even if they already started chelation for this indication. Novartis will interact with local networks to ensure targeting the best representation as possible. Therefore, no limitation of potential selection bias is expected in this trial.

The limitations of the research may be a small sample size.

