10.5.3.2 Adverse events (AEs)

Summary tables for adverse events (AEs) will include only AEs that started or worsened during the on-treatment period, the ***treatment-emergent*** AEs.

The incidence of treatment-emergent adverse events (new or worsening from baseline) will be summarized by system organ class and or preferred term, severity, type of adverse event, relation to study treatment.

Serious adverse events and non-serious adverse events and adverse events of special interest (AESI: including esophagitis, stomatitis, mouth ulceration, gastric ulcers, hemorrhage, abdominal pain, diarrhea, nausea and vomiting) during the on-treatment period will be tabulated. The number and frequency of overall AEs and gastrointestinal AEs will be summarized for naïve (no ICT prior to enrollment) and non-naïve patients.

All deaths (on-treatment and post-treatment) will be summarized.

All AEs, deaths and serious adverse events (including those from the pre and post-treatment periods) will be listed and those collected during the pre-treatment and post-treatment period will be flagged.

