2.8.2 Statistical hypothesis, model, and method of analysis

Proportion of patients with selected GI disorders will be provided together with the corresponding 95% confidence interval using the Clopper-Pearson exact method for this proportion (see [section 5.3.1](#)).

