2.11.2 Subgroup analysis

Not Applicable

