For the palatability questionnaire, standard descriptive analyses based on the derived scores will be provided at screening visit 1 (baseline), week 4, week 12, and EOT, as well as their changes from baseline at week 4, week 12, and EOT for patients pre-treated with deferasirox. For the Chelation naïve patients and patients treated with chelation therapy other than deferasirox who stopped chelation treatment more than 7 days prior to Screening visit, only descriptive statistics by visit will be provided. The standard descriptive analyses include: n, mean, standard deviation, minimum, median, and maximum. The 95% confidence intervals will be presented for the mean changes from baseline at week 4 and week 12 and EOT for patients pre-treated with deferasirox.

Box plot will be presented to summarize the scores graphically at week 4, week 12 and EOT.

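### SAP Section 4 withdraws, without a reason, the protocol's descriptive summary of overall and GI adverse events by prior chelation status

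*SAP*

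**What the plan says.** Protocol 10.5.3.2: "The number and frequency of overall AEs and gastrointestinal AEs will be summarized for naïve (no ICT prior to enrollment) and non-naïve patients". Naïve there means no chelation at all before enrolment, so the non-naïve group combines children already on deferasirox with children coming from deferoxamine or deferiprone.

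SAP Section 4, first bullet, repeats this commitment and adds "However, this will not be done". The same bullet goes on to a separate change, that only on-treatment deaths will be summarised. The second bullet, on ECG, auditory and ocular data, gives its reason (little data collected). The first bullet gives none.

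SAP 2.3 and 2.11.2 are both marked not applicable. The SAP change log attributes the 2.11.2 entry to consistency with the protocol.

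The primary analysis is a single figure in all treated children: "Proportion of patients with selected GI disorders will be provided together with the corresponding 95% confidence interval using the Clopper-Pearson exact method" (SAP 2.8.2). Protocol 10.4.2 has the same pooled proportion.

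Protocol 5.2 and 5.3 admit children continuing deferasirox, children switching from another chelator and chelation-naïve children, with no quota. Exclusion 3 removes children with "Unresolved adverse events if the patient was previously treated with deferiprone or deferoxamine or deferasirox".

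For the caregiver questionnaires the SAP does keep a split by prior therapy, for example "as well as their changes from baseline at week 4, week 12, and EOT for patients pre-treated with deferasirox" (SAP 2.13.2).

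**The concern.** The study answers a regulator's request to characterise GI safety of the crushed tablet in the youngest children. The three kinds of entrant differ by design in ways that could bear on GI events. Entry ferritin thresholds differ (protocol 5.2, criteria 4 and 5), as do the basis for the starting dose (6.1) and the timing of ferritin-driven dose changes (6.3.1.4). Protocol 1.2.1.2 describes GI reactions as dose-dependent and generally transient, so earlier exposure may matter as well.

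A pooled proportion is a weighted average whose weights are whatever mix happens to enrol. A reader who wants the rate for a child starting deferasirox would look for a breakdown by prior therapy. The protocol offered a partial one; under the SAP there is none. The change log's explanation does not help, because the protocol section with which the SAP should be consistent is the one that plans the summary.

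**Working it through.** **1. Is another adverse event table split by prior therapy?** No.
- SAP 2.11.1 tabulates by system organ class, preferred term, severity and relationship.
- SAP 2.11.1.1 tabulates events of special interest by grouping and preferred term.
- SAP 2.8.4 gives exposure-adjusted incidence by severity and preferred term.
- SAP 2.7.1.1 summarises and lists prior chelation, but does not cross it with events.

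**2. The plan's own figures.** For n = 40, P(at least one event) = 1 − (1 − p)^40. At p = 3% this is 1 − 0.97^40 = 0.704 (stated 0.70). The Clopper-Pearson interval for 4/40 is 2.8% to 23.7% (stated 0.03 to 0.24). All ten rows of SAP Table 3-1 reproduce to two decimals, so the sample size figures are not in dispute.

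**3. How far could pooling move the rate?** The documents give neither GI rates by prior therapy nor the expected mix, so this is an illustration. Let w be the share on deferasirox at entry, c their GI rate and s the rate in children new to deferasirox. Then

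pooled = w × c + (1 − w) × s.

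Assume s = 40%, borrowing the roughly 40% GI rate of the paediatric observational studies (protocol 1.2). Assume c = 10%, 20% or 26%, the last borrowed from protocol 1.2.1.2. Neither source figure is broken down by prior therapy.

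| c | w = 25% | w = 50% | w = 75% |
|---|---|---|---|
| 10% | 32.5% | 25.0% | 17.5% |
| 20% | 35.0% | 30.0% | 25.0% |
| 26% | 36.5% | 33.0% | 29.5% |
| 40% (no difference) | 40.0% | 40.0% | 40.0% |

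Where the groups differ, the pooled rate lies between 40 − 36.5 = 3.5 and 40 − 17.5 = 22.5 points below the new-user rate. In one of those nine cells (c = 10%, w = 75%, i.e. 7/40) the pooled exact interval, 7.3% to 32.8%, excludes 40%. In the other eight it includes 40%.

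With whole counts: 9/20 new users (45%; 23.1% to 68.5%) and 4/20 continuing users (20%; 5.7% to 43.7%) pool to 13/40 = 32.5% (18.6% to 49.1%). With 70% continuing users, the same rates pool to 0.7 × 20% + 0.3 × 45% = 27.5%. The 45% and 20% are invented for the example.

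**4. What would a restored table show?** At an observed 40%, the exact intervals are 12.2% to 73.8% (4/10), 19.1% to 63.9% (8/20) and 22.7% to 59.4% (12/30). The chance of seeing at least one case of a 3% event is 0.70 at n = 40, 0.60 at n = 30, 0.46 at n = 20 and 0.26 at n = 10. Rows of this size support description, not comparison.

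**The case against.** Several points against the concern stand.

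- The primary endpoint was one pooled proportion in the protocol. Pooling fits the stated population, which expressly includes children continuing deferasirox. A reader might infer that the SAP change causes the mixing; it does not.
- The withdrawn split is naïve against any prior chelation. The protocol never promised a continuing-versus-new-to-deferasirox split of adverse events, so the lack of one is not a broken commitment.
- A reader might infer that children on deferasirox at entry have been shown to tolerate it. That is only plausible. Exclusion 3 also screens switchers, it does not exclude resolved GI events, and exclusion 9 removes uncontrolled nausea, vomiting or diarrhoea in every group. Tolerating another form is not tolerating the crushed tablet.
- The questionnaire groups are not a ready-made flag. They set naïve children, together with those who stopped another chelator more than 7 days before screening, against children pre-treated with deferasirox. A child still on another chelator at screening fits neither group.
- The change is openly declared, the SAP places its decisions before database lock, and adverse events and prior chelation are both listed by patient. The split could be rebuilt by hand for about 40 children.

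The objection does not supply a reason for the withdrawal. Small numbers would explain it poorly, since the SAP keeps a split by prior therapy for the questionnaires. Leaving readers to rebuild a planned table from listings does not replace the table.

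**Conclusion.** The point holds in a limited form. A protocol-planned descriptive safety summary is withdrawn without a reason, and the one explanation nearby, in the change log, conflicts with protocol 10.5.3.2. What is lost is the only planned adverse event table that would partly show whether GI risk differs by prior therapy.

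The size of any dilution of the new-user rate is unknown and may be nil. The 3.5 to 22.5 points rest wholly on assumed rates and shares. The documents do not support saying that the primary rate is biased, or that it cannot be applied to a child starting the drug: in most of the assumed scenarios its interval still covers the new-user rate.

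Protocol 7.2.3 says "Therefore, no limitation of potential selection bias is expected in this trial". A reader might treat the missing table as a failure to test that statement. The statement concerns the choice of sites and patients, and a table by prior therapy would not test representativeness. Its wording is a separate matter.

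**What to change.** In SAP Section 4, delete only the two sentences on the naïve/non-naïve summary. Keep the deaths text in that bullet, with its reference to protocol 10.5.3.2.

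Restore the table for overall adverse events, GI adverse events and the primary endpoint, giving n, % and exact 95% interval, without testing. Use three rows beside the pooled result:

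1. chelation-naïve;
2. switching from another chelator;
3. on deferasirox at entry.

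Row 1 against rows 2 and 3 gives the protocol's split. Rows 1 and 2 against row 3 separate children starting deferasirox from those continuing it. Declare the added row split in Section 4, since it goes beyond the protocol. Derive the groups from the prior-chelation records described in SAP 2.7.1.1, and state beforehand where a child with past but no current chelation, or with earlier deferasirox use, belongs. Bring SAP 2.3 and 2.11.2 into line.

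The cost is one descriptive table from data already collected, with wide intervals in each row. No change to protocol 7.2.3 is needed for this.

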¹ History of prior transfusion up to 3 months prior to Screening visit 1 (SV1) must be collected at SV1. Additionally, record of transfusion during the study must be collected.

² The choice of method for ocular and auditory assessments will be at the discretion of the investigators. Best efforts should be made to perform these assessments in all subjects, although feasibility in very young children will be at the discretion of the investigator.

³ Chelation naïve patients and patients treated with chelation therapy other than deferasirox who stopped chelation treatment more than 7 days prior to Screening visit 1 (SV1) will not complete questionnaires at SV1.

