7.2.2.6 Ocular assessments

Ocular assessments will be performed at screening visit 1 and at end of treatment according to the local (institution's) clinical practice. The choice of method for ocular assessments will be at the discretion of the investigators. Best efforts should be made to perform these assessments in all subjects, although feasibility in very young children will be at the discretion of the investigator. Additional ocular assessment is permitted at the discretion of the Investigator based on patient reporting of symptoms.

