7.2.2.7 Auditory assessments

Auditory assessments will be performed at screening visit 1 and at end of treatment according to local (institution's) clinical practice. The choice of method for auditory assessments will be at the discretion of the investigators. Best efforts should be made to perform these assessments in all subjects, although feasibility in very young children will be at the discretion of the investigator. Additional auditory assessment is permitted at the discretion of the Investigator based on patient reporting of symptoms.

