10.5 Secondary objectives

Evaluate AEs suspected to be related to the crushed deferasirox FCT:

- Number and percentage of patients who experienced AEs suspected to be related to the study drug up to 24 weeks including 30 day safety follow-up overall and by SOC.

To assess the overall safety of crushed deferasirox FCT:

- Number and percentage of patients with any AEs, SAEs, and AEs leading to discontinuation together with their severity up to 24 weeks including 30 days safety follow-up will be provided. Details regarding the analysis of AEs are described in [Section 10.5.3.2](#).
- Absolute change from baseline over time as box plots for serum creatinine, creatinine clearance, UPCR, total bilirubin, ALP, ALT, AST will be provided. Furthermore, shift tables using low/normal/high classification will be provided. Details regarding lab abnormalities are described in [Section 10.5.3.3](#).
- Other safety data (e.g., ECGs, vital signs, ocular, auditory examinations) will be descriptively summarized.

To assess the efficacy of deferasirox FCT treatment:

- Absolute change from baseline over time in SF values up to 24 weeks of treatment will be provided

To evaluate patient treatment satisfaction, palatability and GI symptoms with ObsROs

- Please refer to [Section 10.5.7](#).

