10.5.3.4 Other safety data

Data on ECG, vital signs, height, weight, ocular and auditory findings will be listed, summarized and flagged as appropriate. Any significant findings after the start of the study will be documented as AEs and reported as such.

Summary statistics of the number of transfusions, average amount RBC (in mL/kg/day) transfused per patient, as well as the average iron intake (in mg/kg/day) will be provided.

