1.2 Study objectives and endpoints

The study objectives and endpoints are described in the following table:

Table 1-1 Study objectives and endpoints

Objective	Endpoint
Primary	

To assess the safety of crushed deferasirox FCT with respect to selected gastrointestinal (GI) disorders in pediatric patients aged ≥ 2 to < 6 years with transfusional iron overload up to 24 weeks including 30 days safety follow up	Number and percentage of patients with selected gastrointestinal disorders (esophagitis, stomatitis, mouth ulceration, gastric ulcers, hemorrhage, abdominal pain, diarrhea, nausea, and vomiting) up to 24 weeks including 30 days safety follow-up
Secondary	
Evaluate AEs suspected to be related to the crushed deferasirox FCT	Number and percentage of patients who experienced AEs suspected to be related to study treatment up to 24 weeks including a 30 day follow up overall and by SOC.
To assess the overall safety of crushed FCT of deferasirox	Overall safety up to 24 weeks including 30 days safety follow-up as measured by frequency and severity of adverse events, serious adverse events (SAEs) and AEs leading to discontinuation and absolute change from baseline over time (shift tables will also be provided) for serum creatinine, creatinine clearance, UPCR, total bilirubin, ALP, ALT, AST). Other safety data (e.g., ECGs, vital signs, ocular, auditory examinations) will also be summarized.
To assess the efficacy of deferasirox FCT treatment	Change from baseline over time in SF up to 24 weeks of treatment
To evaluate patient treatment satisfaction, palatability, and GI symptoms with Observer-reported Outcomes (ObsROs)	Domain scores with ObsROs (Modified Satisfaction with Iron Chelation Therapy [mSICT], palatability, and GI symptom) questionnaires

2 Statistical methods

This section contains information that will be used to draft CSR Section 9.7 on statistical analysis.

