2.11.5.3 Auditory and ocular findings

Auditory and ocular exams will be performed at screening, EOT and as needed basis. Auditory data will be listed using the Safety set. The listing will include the date when the tests were performed, overall interpretation of the test and any clinical significant abnormality findings.

Ocular data will also be listed using the Safety set. The listing will include the date of assessment performed, overall interpretation and any clinical significant abnormality findings.

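### SAP section 4 moves post-baseline hearing and eye results to listings for a reason that fits ECG but not these tests, so no planned table shows how many children were tested at both visits

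*SAP*

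**What the plan says.** The protocol places ocular and auditory examinations within the secondary overall-safety endpoint. Protocol section 10.5 states: "Other safety data (e.g., ECGs, vital signs, ocular, auditory examinations) will be descriptively summarized". Protocol section 10.5.3.4 says that "ocular and auditory findings will be listed, summarized and flagged as appropriate". SAP Table 1-1 repeats the commitment: "Other safety data (e.g., ECGs, vital signs, ocular, auditory examinations) will also be summarized".

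SAP section 4 (Change to protocol specified analyses) departs from this: "ECG, auditory and ocular findings are only listed but not summarized due to the limited amount of data collected". In parentheses it gives the grounds: post-baseline ECGs are unscheduled only, and post-baseline ocular and auditory data come mainly from the end-of-treatment visit. SAP section 2.11.5.3 follows suit and plans listings only. SAP section 2.5 still summarizes the baseline interpretation of the audiometric and ocular tests (normal, or abnormal and clinically significant or not).

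On the schedule, protocol section 7.2.2.6 says "Ocular assessments will be performed at screening visit 1 and at end of treatment" and section 7.2.2.7 says "Auditory assessments will be performed at screening visit 1 and at end of treatment". SAP section 2.11.5.3 agrees: "Auditory and ocular exams will be performed at screening, EOT and as needed basis". Footnote 2 to protocol Table 7-1 asks for best efforts in all subjects, "although feasibility in very young children will be at the discretion of the investigator". Protocol section 7.2.2.10.1 schedules the ECG at screening visit 1 only.

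**The concern.** One reason is used for three assessments, and it fits only one of them. With no scheduled post-baseline ECG, there is little to tabulate. For hearing and eyes, data that come mainly from end of treatment are what the schedule is designed to produce: one result before treatment and one after.

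What is lost is a denominator. Decreased hearing and lens opacities are named as reported with the drug in protocol section 6.3.1.9, and the study exists to characterize safety in the youngest children. If the report says that no new hearing or eye abnormality was seen, readers will tend to set that against all treated children. The evidence comes only from children tested at both visits, who may be fewer because testing may be skipped in the very young. No planned table gives that number.

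**Working it through.** **Step 1. The three assessments side by side.**

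| | ECG | Hearing | Eyes |
|---|---|---|---|
| Scheduled before treatment | Screening visit 1 | Screening visit 1 | Screening visit 1 |
| Scheduled after baseline | None | End of treatment | End of treatment |
| Baseline output (SAP 2.5) | Summary and listing | Summary and listing | Summary and listing |
| Post-baseline output (SAP 4; 2.11.5.1.2, 2.11.5.3) | Listing | Listing | Listing |
| Paired table possible from scheduled data | No | Yes | Yes |

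Children who stop early are also due an end-of-treatment visit within 7 days with the final-visit assessments (protocol sections 4.1 and 7.1.5), so early stopping does not by itself remove the second test.

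**Step 2. Does another planned output give the number tested at both visits?** SAP 2.5 can show how many had a baseline result, but not how many had a pair. Adverse-event tables take the number of patients in the relevant population as denominator (SAP 2.1.1), here all treated children. That is right for adverse events, but it does not separate tested-and-normal from not-tested. A change from normal to an abnormality judged not clinically significant need not become an adverse event, so it may appear only in the listings. The dated listings in SAP 2.11.5.3 allow the count to be made by hand.

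**Step 3. The plan's own figures.** SAP Table 3-1 (protocol Table 10-1) uses P(at least one) = 1 − (1 − p)^40. At p = 0.03 this is 0.704, stated as 0.70. At p = 0.05 it is 0.871, stated as 0.87. The Clopper-Pearson interval at 5% (x = 2, n = 40) is 0.006 to 0.169, stated as 0.01 to 0.17. All ten rows reproduce to two decimals.

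**Step 4. How much the denominator matters.** Let k be the number tested at both visits, and suppose none of them was abnormal at screening. With no new abnormality, the Clopper-Pearson 95% upper limit is 1 − 0.025^(1/k) (the x = 0 case in SAP 5.3.1). The chance of seeing at least one child with a finding of 5% incidence is 1 − 0.95^k. The value 40 is the planned minimum enrolment; 30, 20 and 10 are assumptions, since the documents do not give k.

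| k | Upper limit with 0 of k | Chance of at least one at 5% incidence |
|---|---|---|
| 40 | 8.8% | 0.87 |
| 30 | 11.6% | 0.79 |
| 20 | 16.8% | 0.64 |
| 10 | 30.8% | 0.40 |

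A null result in 20 children is compatible with nearly twice the incidence of one in 40 (16.8 / 8.8 = 1.9).

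**The case against.** The sponsor can answer on several grounds, and much of the answer stands.

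- The change is open. SAP section 4 cites protocol 10.5.3.4, says what will change and why, and agrees with SAP 2.11.5.3. Table 1-1 merely restates the protocol endpoint. This stands: a reader might infer a concealed change, and the documents do not support that. The qualifier in 10.5.3.4 about appropriateness gives some latitude, although protocol 10.5 promises the summary without it.
- No result disappears. Listings carry test dates and interpretations, and significant findings are recorded as adverse events. This also stands. A reader might infer that adverse-event counts are wrong or that safety signals would be lost; neither follows.
- The argument seems to pull both ways: if many tests are skipped, data really are limited. But the SAP's stated reason is when the tests fall, not how many are missing. If many are missing, that is a reason to print the count.
- The values of k are hypothetical, and best efforts are required in all subjects. Correct. A reader might infer that few children will have been tested; nothing in the documents shows that.
- Test methods follow local practice, so pooled results mix methods. This is a real limitation that deserves a footnote. It does not prevent a table, because SAP 2.5 already pools baseline results on a common interpretation scale.
- Protocol Table 6-4 describes testing before treatment as required, without mentioning the discretion elsewhere. That is a separate matter of conduct and would need a protocol amendment. It is not part of this point.

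**Conclusion.** The point holds as a minor inconsistency with a small reporting consequence. The reason in SAP section 4 justifies listing-only for ECG but not for hearing and eye tests, and for those tests SAP section 4 conflicts with SAP Table 1-1 and with protocol sections 10.5 and 10.5.3.4. What is missing is a post-baseline summary and the number of children tested at both visits.

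The size depends on that unknown number. If nearly all children are tested twice, the omission costs almost nothing. If half of the minimum 40 are, the upper limit behind a null result rises from 8.8% to 16.8%. The conclusion rests on the schedule and planned outputs as written and assumes nothing about how many tests were actually done. The primary gastrointestinal rate and the adverse-event counts are unaffected.

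**What to change.** - **SAP section 4:** keep listing-only for ECG; remove it for auditory and ocular findings.
- **SAP section 2.11.5.3:** add one descriptive shift table per test on the Safety Set, screening result by end-of-treatment result. Use four categories at each visit: normal, abnormal not clinically significant, abnormal clinically significant, not done. Show the number tested at both visits, and footnote that test methods followed local practice.
- **SAP Table 1-1:** the change above brings SAP section 4 back into line with the table for hearing and eyes. Amend the table's ECG wording to match SAP section 4.

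No confidence interval is needed, since the protocol promised only a descriptive summary. Protocol Table 6-4 need not change.

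The cost is two small tables from results already destined for the listings, using the interpretation scale in SAP 2.5 plus a not-done category. No extra test or visit is needed, and no protocol amendment, because the protocol already specifies the summary.
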